10.8.2.3 Involuntary Withdrawal

A subject also may be withdrawn by the investigator if the subject's participation in the study will have a negative effect on the safety of the subject. Data obtained up to the date of the subject's withdrawal will be included in the study, if applicable.

10.8.2.4 End of Study

Subjects may exit the study at the end of the study (i.e., the study is discontinued by the Sponsor) or when the subject has completed the 3-year follow-up visit, whichever comes first, unless the subject opted to undergo an alternative BPH treatment. Subjects who receive an alternative BPH treatment will exit the study after the 6 months follow-up evaluation.

An End of Study CRF will be completed at the time the study is completed, discontinued, or lost to follow-up for each subject.

11 Subject Evaluation Description

11.1 Subject Questionnaires

All questionnaires are self-administered and will be completed at baseline (if applicable) and at the required follow-up visit. Questionnaires completed at baseline will be compared to those completed at follow-up visits to assess the effect of treatment. The major instruments and assessments administered are described in this section.

11.1.1 IPSS (Standard)

The IPSS contains the well-validated, highly reliable and responsive American Urological Association symptom score (AUA-SI) assessment to identify the severity of BPH symptoms. The first seven questions in the IPSS address frequency, nocturia, weak urinary stream, hesitancy, intermittence, incomplete emptying, and urgency, and scored on a 6-point scale (0 to 5). Patients are asked to respond relative to the statement of “During the last month or so how often have you had.....” (each symptom category) - Not at all, Less than 1 time in 5, Less than 1/2 the time, About 1/2 the time, More than 1/2 the time or Almost always. Although there are no standard recommendations for grading patients with mild, moderate, or severe symptoms, patients can be generally classified as follows: 0-7 mildly symptomatic, 8-19 moderately symptomatic, and 20-35 severely symptomatic.

The IPSS also includes the following eighth question that is designed to assess the degree of "bother" associated with the subject's urinary symptoms: "If you were to spend the rest of your life with your urinary condition just the way it is now, how would you feel about that?" Answers range from "delighted" to "terrible" (0-6). This question correlates well with the overall BPH symptom score and summarizes the impact of urologic symptoms on quality of life.

The standard IPSS will be administered at baseline and at each follow-up visit, except the two and four week follow-up.

11.1.2 International Prostate Symptom Score (Acute)

The acute IPSS is the same as the standard IPSS except that the questions refer to the subject's condition in the past week instead of the past month. This IPSS will be administered at the 2 week follow-up visit and if indicated, at unscheduled visits.

11.1.3 BPH Impact Index

The BPHII was developed for use in conjunction with the IPSS for men experiencing “lower urinary tract symptoms” (LUTS). The BPHII contains four questions designed to assess the level of physical discomfort, worry, how bothersome the symptoms are, and the level of interference with the subject's daily activities, each scored on a scale from 0-4.

11.1.4 International Index of Erectile Function

The IIEF is a standardized 15-question, validated, multi-dimensional, self-administrated questionnaire has been found to be useful in the clinical assessment of erectile dysfunction. A score of 0-5 is awarded to each of the 15 questions that examine the 4 main domains of male sexual function: erectile function (Q1,2,3,4,5,15), orgasmic function (Q 9,10), sexual desire (Q 11,12),

intercourse satisfaction (Q 6,7,8) plus overall satisfaction domain(Q 13,14). Question responses are relative to performance over the past 4 weeks. The IIEF-15 total score is the sum of the ordinal responses to the 5 domains.

11.1.5 Male Sexual Health Questionnaire Short Form

The MSHQ-EjD Short Form is an abridged version of the 25-item MSHQ. It is a standardized 4-item, validated, self-administrated questionnaire used to assess ejaculation dysfunction. Patient responses are relative to performance “in the past month” related to ejaculatory function in 3 domains (frequency, force, volume) and an independent ejaculatory bother domain.

11.1.6 Eq-5D-5L

The EQ-5D-5L consists of 2 pages – descriptive system (page 1) and the EQ Visual Analogue scale (EQ VAS) (page 2). The descriptive system comprises 5 dimensions (mobility, self-care, usual activities, pain/discomfort, and anxiety/depression) with each dimension having 5 levels: no problems, slight problems, moderate problems, severe problems, and extreme problems. The EQ VAS records the respondent’s self-rated health on a 20cm vertical, visual analogue scale with endpoints labelled ‘the best health you can imagine’ and ‘the worst health you can imagine’.

11.1.7 Patient Global Impression of Improvement (PGI-I)

The PGI-I is a single question transition scale asking the patient to rate their urinary tract condition now, as compared with how it was prior to beginning treatment on a scale from “1-Very much better” to “7- Very much worse”.

11.1.8 Subject Pain Questionnaire

Pre- and post-procedure pain will be evaluated using a standardized pain questionnaire.

11.1.9 Resumption to Activities

An assessment of when a subject resumed his normal activities after the Rezūm procedure will be evaluated.

11.1.10 Subject Satisfaction Questionnaire

The Subject Satisfaction Questionnaire queries the subjects about their impressions of the treatment.

11.2 Urodynamics

Urodynamic testing evaluates how well the bladder, sphincters, and urethra are storing and releasing urine. Urodynamic tests focus on the bladder’s ability to hold urine and empty steadily and completely. Urodynamic tests also can show whether the bladder is having involuntary contractions that cause urine leakage.

Within the study, all subjects will undergo baseline urodynamic testing to evaluate the bladders function and efficiency. The voiding pressure-flow study helps assess two critical factors related to the bladder, bladder neck and prostate: detrusor activity (normal vs. impaired) and outlet resistance (obstructed vs. unobstructed). Poor detrusor muscle function is defined as any subject with bladder outlet obstruction, calculated from the urodynamic tracings, accompanied by

impaired detrusor underactivity who fall below the 25th percentile of accepted and established nomograms.

Procedure: A repeat free uroflowmetry procedure is performed and the patient is placed in lithotomy position to insert a 6 or 7 French dual lumen urodynamics catheter. Air charged (T-Doc) urodynamic catheters will be used for reliability of testing and standardized for all study centers. Using a large syringe, the bladder will be emptied to obtain an accurate post-void residual urine volume (this sample may be utilized for urinalysis per protocol). A 10-French rectal balloon catheter, to monitor abdominal pressure, will be placed 10 cm above the internal rectal sphincter.

During the filling phase of the cystometrogram, it is important to assess the sensory response of the patient. The technician will instruct the subject in the following steps:

- **First Sensation:** When is the first sense of bladder filling?
- **First Desire:** When is the first desire to void, such as when the subject might consider pulling off the highway at the next available service station?
- **Strong Desire:** When is the definite desire to find the next restroom?

It is usually easier to leave the patient in the lithotomy position during the filling phase.

The emptying pressure-flow measurement should be performed in the subject's preferred position-standing or sitting. It is vital to make sure all the pressure monitors are functioning properly and usually a "cough test" will demonstrate this function. It is often preferred to allow the subject to void in private for best pelvic relaxation. It is vitally important that complete confidence exists in the registering of both abdominal, detrusor and uroflow catheters, transducers and computer tracings. If there is any question about any of these factors, the urodynamic study should be repeated after correcting any defects.

The urodynamic voiding pressure-flow study makes a precise diagnosis of obstruction in men and assumes the outcome of prostate tissue reduction and consequent LUTS will improve when obstruction is documented. It is difficult to diagnose obstruction in the face of detrusor underactivity (DU). Impaired contractility results from long-term obstruction and BOOI must be at least 40 cm H₂O to be able to confirm adequate contractility of the bladder [21]. An International Continence Society (ICS) nomogram can exclude obstructed patients who have impaired contractility. This requires clinical judgment in selecting patients for treatment, but typically reduced compliance of the bladder is improved after treatment of the BPH.

The bladder outlet obstruction index (BOOI) is calculated from the urodynamic tracings.
 $P_{det} = P_{ves} - P_{abd}$; $BOOI = P_{det} Q_{max} - 2Q_{max}$ [cm H₂O]

Bladder contractility index (BCI) is calculated: $P_{det}Q_{max} + 5(Q_{max})$. This value is greater than 150 in a strong contracting bladder, 100-150 in normal bladder, and less than 100 in a weak bladder. This corresponds to the ICS nomogram.

All tracings will be submitted for analysis by an independent reviewer.

11.3 Uroflowmetry

Recommendations of the International Incontinence Society (ICS) Good Urodynamics Practices protocol will be used for this study.

Subjects will be asked to hydrate and refrain from voiding for two hours. Hydration may be achieved by asking the subject to drink 2 or more cups of non-caffeinated fluids.

General Instructions for Uroflowmetry:

- It is preferred that the measurements be performed in the standing position. All subsequent measures should be performed in the same position as was used for the baseline assessment.
- Men should have a sense of bladder fullness and express a desire to void prior to micturition testing.
- Fullness of the bladder will be assessed by ultrasound; urine volume must be from ≥ 250 to ≤ 550 mL prior to uroflow determination.
- Uroflowmetry will be performed using a standard calibrated flowmeter.
- Recording will start at initiation of voiding
- Parameters will be calculated by the flowmeter, and the printout of the record will be photocopied and retained.
- Uroflowmetry results will be considered valid only if the pre-void total bladder volume (assess by ultrasound) was ≥ 250 to ≤ 550 mL and the voided volume was ≥ 125 mL.
- Retests will be allowed only in the event of small voided volume (< 125 mL) or uroflowmeter malfunction.

Adequate privacy should be provided and patients should be asked to void when they feel a “normal” desire to void. Patients should be asked if their voiding was representative of their usual voiding and their view should be documented.

To qualify for entry into the study the following measurements must be achieved:

- Voided volume (≥ 125 ml required to be eligible for the study);
- Peak flow rate, Q_{max} (≥ 5 ml/sec to < 12 ml/sec to qualify) averaged over a 2 second interval;
- Average flow rate;
- Voiding time.

11.3.1 Peak Flow Rate (Q_{max}) Measurement

The recommendation for determining Q_{max} is to apply the 2 second-rule to improve consistency, which avoids artifacts in the reading.

11.3.2 Post Void Residual Urine Volume

Following uroflowmetry, residual urine volume in the bladder will be assessed by bladder scanner ultrasound. It is recommended that PVR be obtained with urodynamic testing catheter after voiding just prior to the urodynamic pressure-flow study.

Voiding efficiency (VE) is calculated to determine percentage of bladder emptying in relation to bladder filling volume: $VE = (\text{voided volume}/\text{bladder capacity}) \times 100\%$.

All tracings and printouts of uroflowmetry and post-void ultrasound shall be submitted to an independent reviewer for reading, calculations and entry into the case report form. Multiple data points can be reported from noninvasive uroflowmetry. These include the following:

- Voided volume (VV in milliliters)
- Flow rate (Qmax in milliliters per second)
- Maximum flow rate (Qmax in milliliters per second)
- Average flow rate (Qave in milliliters per second)
- Voiding time (total time during micturition in seconds)
- Flow time (the time during which flow occurred in seconds)
- Time to maximum flow (onset of flow to Qmax in seconds)

Interpretation of Uroflowmetry Data

- Baseline uroflowmetry data will be interpreted by the principal investigator to assess subject eligibility (Inclusion criteria 3 and exclusionary criterion 10);
- Data for all protocol required follow-up visits thereafter will be read by an independent reviewer;
- All efficacy analyses will be performed using the independent reviewer's assessments.

11.4 Flexible Cystoscopy

A screening flexible cystoscopy will be performed to check for the integrity of the bladder, urethral abnormalities, strictures, prostatic urethral configuration, presence of median lobe within the bladder, and to gauge how much of the prostate protrudes into the bladder (defined as intravesical prostatic protrusion). It is recommended that all air bubbles be expelled to assure quality video monitoring.

A post-treatment flexible cystoscopy will be performed immediately post procedure and at the 6-month follow-up visit after other evaluations are completed. All cystoscopies are to be video-recorded and forwarded to the sponsor. A copy of these recordings will be provided to the Clinical Events Committee (CEC) for a review of potential Adverse Events.

11.5 Digital Rectal Exam

A digital rectal exam (DRE) will be used to screen for malignant prostate tissue.

11.6 Transabdominal and Transrectal Ultrasound

The primary purpose of ultrasound imaging in this study is to determine prostate size and the presence of any intravesical prostatic protrusion. There is a very high correlation between an IPP with bladder outlet obstruction (BOO). Studies of transabdominal (TAUS) and transrectal (TRUS) ultrasound [22-24] show three grades of distance between the tip of prostatic intrusion and base of the bladder.

These grades correlate very well with PSA and degree of LUTS due to BPH:

- ≤ 5 mm is grade I,
- >5 to 10mm is grade II, and

- >10mm is grade III

The lobar anatomy has been well demonstrated utilizing resolution of 3-T MRI imaging [25].

The TAUS will be performed with approximately 150 mLs of urine in the bladder. Bladder wall thickness also can be described and combined with flexible cystoscopy observation. The distance from the tip of the prostatic protrusion to the circumscribed base of the bladder is measured in millimeters.

A TRUS will be used to assess the prostate volume, prostatic urethral length and transverse width and general condition of the prostatic tissue. This will be performed at baseline and at different post-treatment follow-ups. To ensure reliable within-subject measurements of the prostate, TRUS will be standardized. Key elements of TRUS standardization include, but are not limited to:

- Ultrasound equipment and transducer and probe configuration recorded for each examination;
- All configurations (bi-plane, multi-plane, and end-fire probes) are acceptable, provided no change of equipment will take place during study;
- Lateral decubitus position is the preferred patient positioning for TRUS measurement.

The following views are required:

- Transverse view at base of prostate,
- Transverse view at mid-gland,
- Transverse view distal third or apex,
- Longitudinal view mid-plane,
- Longitudinal view right side approximately 30-45 degrees from midline, and
- Longitudinal view left side approximately 30-45 degrees from midline.

Prostate volumes will be determined by the following formula: $\pi/6 \times (\text{transverse diameter} \times \text{anteroposterior diameter} \times \text{cephalocaudal diameter})$.

Hardcopies of these images will be obtained by thermal printer (and then photocopied) or otherwise retained.

All TAUS results will be submitted for analysis by an independent reviewer.

Interpretation of TRUS measurements

- Baseline TRUS data will be interpreted by the principal investigator to assess subject eligibility (Inclusion criteria 5).
- TRUS data for all protocol required follow-up visits thereafter will be read by an independent reviewer.
- All efficacy analyses will be performed using the independent reviewer's assessments.

11.7 Retroperitoneal Ultrasound (Renal and Bladder)

A retroperitoneal ultrasound of the abdomen and pelvis will be performed to assess the patients' urinary tract integrity at pre-procedure baseline, 2 weeks (as applicable) and again at their 6 week follow-up appointment. These retroperitoneal ultrasound imaging studies will be used to determine the study's satisfaction of the primary safety endpoint, in particular the presence of permanent damage to the bladder, trigone, or ureteral orifices. The written request for sonographic examination will include sufficient information directing the examiner to allow for appropriate performance of the ultrasound focusing on the primary safety endpoint criteria listed above. Retroperitoneal ultrasound guidelines (urinary tract and bowel):

Kidney Assessment

- Kidney examination should include transverse and long-axis (sagittal or coronal) views
- Assessment of the cortices and renal pelvises should be made
- The maximum length of each kidney should be recorded
- For vascular kidney examination, Doppler ultrasound can be utilized to assess renal arterial and venous patency and suspected renal artery stenosis
- The kidneys and perirenal regions should be assessed for abnormalities
- Measurements should be taken of any abnormalities

Bladder Assessment

- For examination of the complete urinary tract, transverse and longitudinal (sagittal or coronal) images of the distended urinary bladder should be included if possible
- Abnormalities of the bladder wall or lumen should be noted

Bowel Assessment

- Evaluation of the bowel for wall thickening, dilatation, muscular hypertrophy, masses, vascularity, and other abnormalities can be made
- Identification of bowel perforations or fistulas should be reported

Any site reported abnormalities present on the 2 week (if abnormal BUN or Creatinine) or 6-week ultrasound that were not present at baseline will be reviewed as potential device-related serious complications and a final adjudication will be made by the Clinical Events Committee. The retroperitoneal ultrasound will be used in conjunction with TRUS to adjudicate the potential complications.

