- **Tissue expulsion:** Small pieces of coagulated tissue could potentially slough off after thermal therapy for BPH and possibly cause partial obstruction or even urinary retention. This tissue is usually expelled during urination. This sloughing process may continue for a few months post-procedure depending on the rate of healing. While this is a natural phenomenon, it may cause anxiety and be a nidus for infection.
- Significant **blood pressure elevation** has been reported in other BPH therapies and may occur during treatment. A combination of very short treatment times (e.g., <10 seconds) and the fact that the Rezūm System treatment does not involve the direct application of electromagnetic energy to the prostate tissue mitigates the risk of any clinically significant spike in blood pressure in connection with the procedure. No reports of a significant blood pressure increase have been observed in any clinical trial experience with the Rezūm System.
- Lower urinary tract symptoms present at baseline in BPH subjects may worsen or persist. These symptoms include but are not limited to the following:
 - Dysuria
 - Frequency
 - Urgency
 - Nocturia
 - Acute urinary retention
 - Incontinence
 - Sensation of not emptying bladder completely
 - Urethral stricture
 - Urethritis
 - Irritative urinary symptom
 - Urethral injury causing false passage or adhesion
 - Urinary clot retention
 - Chronic pain in the pelvic area
 - Bladder spasm
 - Hematuria with or without clot in urethra
 - Discharge or cloudy urine
 - Discharge of tissue material during urination
 - Scarring of the urethral system
 - Urinary tract infection
- Other less frequent but potential risks reported with minimally invasive BPH treatments may include:
 - Abscess
 - Damage to bladder floor, trigone, and sphincter
 - Rectal and perineal findings
 - Flu-like symptoms
 - Hematospermia

- Epididymitis
- Flank pain
- Blood loss (> 500 ml)

The full list of anticipated adverse events is provided in Section 14.4. Risks for subjects in this study may be similar to those for subjects being treated with commercially available devices delivering thermal therapy such as the Urologix Prostiva RF device, the AMS Laserscope Greenlight HPS device, the Urologix Targis device, and newer generations of these devices or other TUMT devices.

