9.3.3 Safety Monitoring Early Stopping Rule

An early stopping rule is instituted in the study to monitor the rate of steam-related injury.

This early stopping rule is intended to provide a higher degree of sensitivity to steam-related injury and earlier time-frame than is provided by the primary safety endpoint composite which includes a wider spectrum of adverse events and a longer time period of 6-months post-procedure.

If 2 patients experience a post-procedure CEC-determined device-related steam-related injury requiring intervention within the first 20 subjects treated with Rezūm, the early 6 week post procedure stopping rule is triggered. A threshold of 2 patients with an event out of the first 20 subjects is an observed event rate of 10%.

For the study stopping rule “Intervention” is defined as any surgical procedure or hospitalization performed to remedy or correct a potential permanent damage to the bladder, trigone or ureteral orifices, perforation of the rectum or GI tract, or formation of fistula between the rectum and urethra or bladder.

Irrigation of clot retention or necrotic tissue obstruction is allowed, if medically necessary, and should be reported as an adverse event but will not be counted toward the stopping rule.

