11.8 Genitourinary Perforation and Assessment of Fistula Formation

A urine culture and an abdominal & pelvic exam will be conducted at the 2 and 6 week follow-up visit to assess for potential perforation of the rectum or GI tract; or fistula formation between the urethra and rectum.

The patients also will be asked the following questions:

- 1) Are you passing gas (air) in your urine? Checking for pneumaturia

- 2) Are you seeing any fresh blood in your stool or when you wipe? Checking for hematochezia
- 3) Are you seeing any urine coming from your rectum? Checking for recto-urethral fistulas

If a patient answers yes to any of the three questions, and the patient's urine culture is positive for infection, then the patient will undergo an intravenous rectal and oral contrast CT exam, or any other evaluation method deemed necessary if clinical suspicion exists, to rule out perforation of the GI or GU tracts and/or fistula formation.

12 Statistical Considerations

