12.1 Sample Size Justification

For the trial to be successful, the primary efficacy endpoint must be adequately powered.

For the primary efficacy endpoint to be met, the proportion of the ITT analysis population that responds to therapy must be statistically significantly greater than 50%. A responder is defined as a subject who has an IPSS improvement $\geq 30\%$ post-treatment, as compared to baseline.

The required sample size for this endpoint was calculated based on the following assumptions:

- One-sample exact binomial hypothesis test of proportions,
- Type I error of 0.025, one sided,
- Statistical power of 90%, and
- Population responder rate of at least 67.5%.

The responder rate in the Rezūm II trial was 77.9% (106/136). A population rate of at least 67.5% is selected as a conservative assumption for the responder rate in the Rezūm XL trial based on the lower bound of a two-sided 99% confidence interval for the responder rate in the Rezūm II trial. Based on these assumptions, a sample size of at least 88 intention-to-treat subjects is required for analysis.

Additional subjects may be screened since some subjects that consent may exit the study without being enrolled (e.g. due to withdrawal of consent or not meeting eligibility criteria).

12.2 Primary Safety Endpoint - Post Procedure Device Related Serious Complications:

This safety endpoint will be to demonstrate that the composite rate of post procedure device related serious complications at 6 months is acceptably low.

The following hypothesis will be tested in a one-sided exact binomial test at the 5% significance level.

$$H_0: P_{\text{Rezūm6}} \geq 12\%$$

$$H_1: P_{\text{Rezūm6}} < 12\%$$

Where:

$P_{\text{Rezūm6}}$ is the proportion of subjects experiencing one or more safety composite events within 6 months post-procedure. The safety endpoint is a composite of the four types of events listed below.

Device-related serious complications for this endpoint are defined as:

- Device perforation of the rectum or GI tract
- Device related formation of fistula between the rectum and urethra
- Permanent damage to the bladder, trigone or ureteral orifices requiring intervention
- Grade 2 hydronephrosis

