14.2 Urinary Retention and Obstructive LUTS

14.2.1 Urinary Retention

Urinary retention is the inability to completely empty the bladder and can be acute or chronic.

There are many causations for urinary retention, but BPH in men over the age of 50 account for 53% of the incidence. Neurogenic spinal injury is common, acute prostatitis, medications and pelvic floor disturbance such as urinary external sphincter dyssynergia are other known causes.

Acute urinary retention happens suddenly and lasts only a short time. People with acute urinary retention cannot urinate at all, even though they have a full bladder requiring immediate emergency treatment (i.e., catheterization). Acute urinary retention is an anticipated thermal therapy effect of the Rezūm treatment.

Chronic urinary retention is more insidious and can occur gradually in men with bladder outlet obstruction leading to dysfunctional urinary detrusor with underactivity. This can occur silently over time and can lead to pyelocaliectasis, hydronephrosis with renal insufficiency or failure, bladder and renal calculi and urinary tract infections, occasionally with urosepsis.

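### The primary safety composite is stated as a 6-month rate, but nothing scheduled after week 6 images the kidney or measures renal function, and the dedicated perforation and fistula checks also stop at week 6

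*Combined protocol and SAP*

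**What the plan says.** **The window.** The synopsis (Section 1) tests the composite against 12% at 6 months. In Section 12.2 the tested quantity "is the proportion of subjects experiencing one or more safety composite events within 6 months post-procedure". Section 9.3.3 contrasts the 6-week stopping rule with the composite, which has "a wider spectrum of adverse events and a longer time period of 6-months post-procedure". Section 9.3.2 gives no time point. The components are GI or rectal perforation, recto-urethral fistula, permanent bladder, trigone or ureteral-orifice damage requiring intervention, and Grade 2 hydronephrosis.

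**The dedicated assessments.**
- Retroperitoneal ultrasound: "at pre-procedure baseline, 2 weeks (as applicable) and again at their 6 week follow-up appointment" (Section 11.7). The week-2 scan is done only if BUN or creatinine is abnormal. The same section says: "These retroperitoneal ultrasound imaging studies will be used to determine the study's satisfaction of the primary safety endpoint". The independent review in Section 14.11 covers the same time points.
- BUN and creatinine: baseline and, by column position in Table 10-2, week 2.
- Perforation and fistula: "A urine culture and an abdominal & pelvic exam will be conducted at the 2 and 6 week follow-up visit" (Section 11.8), together with three symptom questions. CT follows only on a positive answer plus a positive culture.

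**What remains after week 6 (Table 10-2).** Adverse event review, physical exam, rectal exam, and uroflow with residual volume take place at 3 and 6 months. TRUS, transabdominal ultrasound and recorded cystoscopy take place at 6 months.

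**The concern.** The endpoint has a 6-month clock, while the assessments written to detect its components, apart from cystoscopy, keep the 6-week clock of the stopping rule. Hydronephrosis matters most because it need not produce symptoms. Section 14.2.1 says of chronic retention: "This can occur silently over time and can lead to pyelocaliectasis, hydronephrosis with renal insufficiency or failure". Section 7.1 adds that shed tissue can obstruct, and that "This sloughing process may continue for a few months post-procedure depending on the rate of healing". Adverse event review finds what a man reports or an examiner notices. It cannot be relied on to find a dilated kidney that causes no complaint.

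The error runs one way. An event that is not looked for is scored as absent, which lowers the observed rate and makes the performance goal easier to meet. What is at stake is whether the trial can claim a 6-month rate for a component that it images only to week 6.

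**Working it through.** **1. The plan's own figure.** Inputs from Sections 12.2 and 9.3.2: N = 88, goal 12%, one-sided exact binomial test at 5%.
- P(X ≤ 5 | 88, 0.12) = 0.0393, which is below 0.05.
- P(X ≤ 6 | 88, 0.12) = 0.0846, which is above 0.05.

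The limit is therefore 5 of 88 (5.7%), as the plan states. The test itself is not in question.

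**2. Share of the window after the last dedicated check.**
- Weeks: (26 − 6)/26 = 0.77.
- Days: 1 − 42/182.6 = 0.77.
- With the visit windows (week 6 ± 7 days, month 6 ± 30 days): 1 − 49/152.6 = 0.68 to 1 − 35/212.6 = 0.84.
- For BUN and creatinine, last drawn at week 2: 1 − 14/182.6 = 0.92.

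The week-2 reading depends on a table extracted from PDF. It fits footnote 3 and Section 11.7, both of which tie the week-2 scan to the blood result.

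**3. Components against what is scheduled after week 6.**

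| Component | Scheduled after week 6 | Specified for that component? |
|---|---|---|
| Grade 2 hydronephrosis | No renal imaging, BUN or creatinine. Residual volume at 3 and 6 months may flag retention | No. Residual volume triggers no renal scan |
| Perforation, fistula | Adverse event review, physical and rectal exam at 3 and 6 months; TRUS and cystoscopy at 6 months | No. Section 11.5 gives the rectal exam a cancer-screening purpose |
| Bladder, trigone, orifice damage | Cystoscopy at 6 months, video to the Clinical Events Committee | Yes (Table 10-2, footnote 2) |

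Section 11.4 describes the 6-month cystoscopy without restriction. Section 10.5.3 limits it to a subset of men who agree.

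**4. Effect on the test.** Let m be the share of composite events that go undetected. At a true rate of 12% the detectable rate is 0.12 × (1 − m), and the chance of passing is P(X ≤ 5 | 88, 0.12 × (1 − m)). The documents give no value for m, so every value below is an assumption. The smaller values take hydronephrosis as a quarter of events with 10%, 20% or 30% of it missed (0.25 × 0.10 = 0.025, and so on). The larger two could arise if it were half of events with 20% or 40% of it missed.

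| m | Detectable rate | Chance of passing |
|---|---|---|
| 0 | 12.0% | 3.9% |
| 2.5% | 11.7% | 4.7% |
| 5% | 11.4% | 5.5% |
| 7.5% | 11.1% | 6.5% |
| 10% | 10.8% | 7.6% |
| 20% | 9.6% | 14.0% |

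One undetected case is enough to turn 6 of 88 (fail) into 5 of 88 (pass).

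**The case against.** Four counter-arguments have weight.

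**Later visits are not empty.** A reader might infer that perforation and fistula go unscreened after week 6. The documents do not support that: the examinations in step 3 could reveal either, TRUS is named in Section 11.7 as an aid to adjudication, and Section 10.5.4 provides for unscheduled visits. What stands is narrower: none of these is specified as a check for those two components.

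**Retention is tracked.** Residual volume at 3 and 6 months follows the precursor through which Section 14.2.1 says hydronephrosis can arise. That section also describes gradual retention in men with outlet obstruction, which is the underlying disease, whereas the endpoint counts device-related events. It shows that late hydronephrosis can be silent. It does not show that late device-related cases will occur.

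**The timing data lean early.** Rezūm II had 3 related serious events in months 0 to 3 and none from then to month 24 (Table 8-9). The pilot's related serious entry is timed to the first month (Table 8-4). These were mostly smaller glands, and neither study summary mentions kidney imaging, so silent cases could have gone unseen. Still, nothing here points to a late excess. The pilot's figure of 75% of adverse events within 30 days does not show that a quarter of composite events come late: it covers all event types and cuts at day 30, not week 6.

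**Large error inflation is not shown.** If 30% of all composite events were missed, the chance of passing would be 24.2%. The evidence of silence concerns hydronephrosis alone, and damage requiring intervention is unlikely to go unnoticed, so the documents give no basis for that share.

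**Conclusion.** The mismatch is real and follows from the schedule alone: a 6-month endpoint, no scheduled renal assessment after week 6, and no dedicated perforation or fistula check after week 6. It is firmest for Grade 2 hydronephrosis and weaker for perforation and fistula, where later general examinations give partial cover.

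About 77% of the window (68% to 84% with visit windows) follows the last dedicated check. That is calendar time. It should not be read as 77% of the risk, since the documents give no hazard over time.

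The direction of bias is certain if any event is missed; its size is not known. Under the assumed shares, the false-pass probability at a true 12% rate moves from 3.9% to between 4.7% and 6.5%, or to 7.6% to 14.0% if 10% to 20% of all events are missed. It passes the nominal 5% at an assumed loss of about 5%. If the true rate is far below 12%, the pass decision hardly depends on this: at 2%, the chance of passing is already 99.1% with full detection. What suffers then is the accuracy of the reported 6-month rate. The point concerns ascertainment and wording. The binomial test and the 5-of-88 rule stand.

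**What to change.** 1. Ask the three Section 11.8 questions at the existing 3- and 6-month visits, and record any positive answer so that it reaches the Clinical Events Committee.
2. Reword Sections 1, 9.3.2 and 12.2 to say that hydronephrosis is screened by imaging to week 6 and counted as reported thereafter to 6 months, and do not present that component as a fully ascertained 6-month rate. Add the missing time point to Section 9.3.2.
3. If the sponsor wants to keep the 6-month claim for hydronephrosis, kidney views at the month-6 ultrasound visit are an option. This is an added procedure: Section 11.6 specifies the transabdominal scan for prostatic protrusion, and kidney views belong to the separate examination in Section 11.7.
4. Reconcile Sections 10.5.3 and 11.4 on who has the 6-month cystoscopy.

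Items 1 and 2 cost three questions at two visits already scheduled, and a slightly less favourable safety statement. They need no extra visit and no change to the sample size or test. Item 3 costs imaging and reading time, which the documents do not allow to be estimated.
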